# **A Study of Cognitive Adaptation Training in Inpatient Forensic Environments**

**PI: [name]**

**Co-PI: [name]**

## **Co-Investigators**

**[name]**

**[name]**

**[name]**

**[name]**

**Version 5.0 – November 18th, 2019**

## **Background**

### ***Overview***

The proposed project will be a mixed-methods feasibility study of modified Cognitive Adaptation Training for an inpatient forensic mental health population (finCAT). Cognitive Adaptation Training (CAT) is an evidence-based compensatory cognitive intervention that focuses on improving functioning through the provision of environmental supports and cues. CAT is typically applied in outpatient care but has been successfully modified for inpatient service contexts in a Netherlands trial and at CAMH in previous pilots for both forensic and non-forensic inpatient populations.

### ***The Impacts of Schizophrenia***

Of the major mental illnesses, which are responsible for 3.8% of hospital admissions in Canada (Health Canada, 2002), schizophrenia is one of the most costly. Though only present in 1% of the general population in Canada, schizophrenia accounts for an estimated \$6.85 billion annually in healthcare costs and lost productivity (Goeree et al., 2005; estimate based upon 2004 data). The impact on the lives of persons with this illness and their social networks are profound. People with schizophrenia typically have a poor quality of life, very low rates of employment, poor social relationships, poor physical health, and extremely high rates of mortality relative to the general population (Brown & Barraclough, 2000).

### ***Cognitive Symptoms of Schizophrenia***

Cognitive deficits are present in 70-75% of patients diagnosed with schizophrenia (Harvey, 2013), and have been shown to have a greater impact on function than either positive or negative symptoms (Keefe & Fenton, 2007). Efforts to address the cognitive impacts of schizophrenia can be broadly defined as falling into either compensatory or restorative categories. Compensatory approaches aim to circumvent cognitive deficits by changing the client's natural environment to support improved functioning. These compensatory strategies serve to bypass cognitive deficits and negative symptoms by organizing belongings and creating reminders and environmental cues to support specific adaptive behaviours. An example includes the packaging of individual items of clothing to be worn by day of the week, to simplify the process of choosing what to wear, decreasing the likelihood of clients impulsively putting on too many clothes, or dressing in a manner that is not a good fit for the weather or social settings (Maples & Velligan, 2008).

### ***Cognitive Adaptation Training (CAT)***

Cognitive Adaptation Training (CAT) is a manualized, compensatory approach pioneered by Dawn Velligan and colleagues that has shown considerable promise as a means to improve treatment adherence and functional outcomes. CAT begins with a neuropsychological assessment of clients to determine the best profile of strategies to be implemented for the particular individual. For example, clients with lower executive functioning likely require greater structure and more obvious visual cues (e.g., bright signs reminding the person to take their medication). Following the assessment, the CAT clinician typically spends 1-2 hours per week with each client developing an individualized profile of strategies based on the toolkit of options outlined in the CAT manual (see Velligan et al., 2000; 2002; 2008a; 2008b; and Draper et al., 2009 for descriptions of the intervention). A well-rounded set of strategies is implemented, modified, and monitored to address key domains such as hygiene, safety, dress, and medication. In past work, the CAT intervention typically lasted for 9 months per person.

Outcomes of randomized trials of CAT have been promising. Compared to control conditions, clients receiving CAT experience lower levels of symptomatology, lower relapse rates, higher levels of adaptive functioning, improved quality of life, and improved medication adherence (Velligan et al., 2000; 2002; 2007; 2008a; 2008b). In general, CAT has been shown to be beneficial for individuals with schizophrenia who vary both in degree and type of functional impairment. It has, however, been found to be more problematic for persons with high levels of paranoia as might be expected given the intensive home-based aspect of the intervention (Maples & Velligan, 2008).

### ***Modified Cognitive Adaptation Training***

Locally, a CAMH study of a modified version of CAT in which an intensive 4-month period of CAT (applied by a CAT Clinician) with 5 months of maintenance (applied by the existing case manager) was recently tested for an outpatient schizophrenia population. This study found a comparable degree of gains in functional domains relative to Velligan's RCTs and those gains were sustained during the case manager led maintenance period (Kidd et al., 2014). This model was also recently tested for an early psychosis population at CAMH with CAT, once again, delivering similar improvements in functional outcomes (Kidd et al., 2019).

### ***Inpatient Settings and Cognitive Adaptation Training***

While the majority of evidence supporting CAT is based on outpatient settings, there is emerging evidence to suggest that CAT may be beneficial to patients with schizophrenia on an inpatient basis as well. Studies in the Netherlands have shown a potential improvement in functioning following an intensive, 1 year period of the full CAT intervention within an inpatient setting (Stiekema et al., 2015, van der Meer, 2017). Our own clinical experience at CAMH suggests that CAT is feasible with an inpatient schizophrenia population (both forensic and non-forensic) with some adjustments to the intervention process, and a greater focus on goals related to room organization and personal hygiene relative to an outpatient population of individuals with the illness. Furthermore, the whole inpatient treatment team is engaged in the intervention, which allows for increased monitoring and modification of environmental supports, and a greater potential for knowledge translation. Evaluation outcomes (not formally researched) of this initial implementation of CAT modified for inpatient units indicated improved room organization and cleanliness amongst 26 recipients. Furthermore, no risks were observed in implementation as evidenced by no increase in code white incidents with evaluation participants, no use of provided environmental supports for violence or unintended purposes, and no incidents involving the evaluation clinician.

At present, there have been no studies examining the implementation of CAT on forensic inpatient units. In Ontario, length of stay varies greatly for individuals with schizophrenia admitted to psychiatric hospitals, with a length of stay ranging between 1 and 3234 days, and an average of stay of 96.6 days (Chen et al., 2017; based on 2005-2015 data). Clients on forensic inpatient units typically demonstrate longer, more predictable lengths of stay compared to an acute population due to Ontario Review Board proceedings and risk management protocols. Our own clinical experience at CAMH suggests that the more predictable length of stay of a forensic inpatient client creates a more stable setting for the delivery of CAT. Attempts to deliver CAT on more acute general psychiatric units have routinely experienced challenges related to unanticipated discharges, clients leaving against medical advice, or transferring to other rooms, units, or hospitals on short notice. Since the CAT intervention depends heavily on engaging a client in their living space, stability in that living space is inherent to the success of the intervention.

The current worldwide body of inpatient research on CAT utilizes specially trained inpatient nursing staff as their primary CAT Clinicians. In contrast, the majority of Canadian research on CAT has utilized occupational therapists as CAT Clinicians. A Canadian study by occupational therapist Raquel Williams et al. (2017) demonstrated that occupational therapists across Canada view CAT as relevant to their practice and scope. At present, there have been no studies examining the implementation of CAT by occupational therapists. Given the relevance of the CAT intervention to the scope and practice of mental health occupational therapists, and the presence of occupational therapists on all inpatient mental health units at CAMH, this staff population would be our primary target to be trained as CAT Unit Champions to support and maintain the delivery of CAT.

### ***The Proposed Project***

The proposed project will expand our knowledge of the role of compensatory cognitive interventions for forensic inpatient populations with schizophrenia. Over the course of 6 months, we will conduct a feasibility study of the delivery of a modified forensic inpatient version of Cognitive Adaptation Training. The objective of this single group study with pre-post and follow up assessments is to determine if preliminary outcomes and follow up findings support the feasibility of a modified version CAT within a forensic inpatient setting. Feasibility data will be used to inform (i) any necessary adjustments to the intervention, (ii) any necessary adjustments to the optimal time of study for outcomes to be observed, and (iii) to inform future trials with respect to anticipated recruitment and drop-out rates and optimal powering.

This study would be among the few examinations of CAT as an inpatient intervention to date, as well as the first to examine a modified cognitive adaptation training approach in both a North American and forensic inpatient setting, and would make a substantial contribution to the evidence-based intervention literature. This intervention will be referred to as forensic inpatient CAT or finCAT.

### ***The questions for this project are:***

#### **(1) Is finCAT feasible for forensic inpatient populations with a schizophrenia spectrum diagnosis?**

Based on preliminary work we hypothesize that finCAT will prove acceptable to patients and inpatient staff and will demonstrate positive outcomes with respect to functioning and inpatient room organization.

**And**

## **(2) What are the attitudes of inpatient forensic occupational therapists and clinical teams towards implementing finCAT on their units?**

### **Methods**

#### ***Study Design Overview***

This study will expand on our preliminary work at CAMH. The study will be implemented on four CAMH general security forensic inpatient units. There will be four weeks of CAT Clinician--delivered treatment focusing on two goal areas – room organization and personal hygiene, followed by two months of maintenance by CAT Unit Champions with pre, post, and two-month follow-up, as well as project-end evaluations. In the first four weeks, we will conduct a trial of finCAT for two of the four inpatient general forensic units, followed by two months of finCAT maintenance with Unit CAT Champions supported by the CAT Clinician. This process would then be repeated on the remaining two general units at CAMH. Previous implementation of CAT has demonstrated gains within one-month; however, follow-up assessments were not conducted to determine if gains were maintained over time. While brief, this time period (i) reflects the intent of this study as a pilot test of feasibility and, (ii) aligns with this circumscribed version of CAT (as compared to the more comprehensive community version with broader outcome domains). Data will be collected from both primary participants (inpatients) and the clinical team.

#### ***Participants***

Participants will be enrolled from four CAMH forensic inpatient units (medium security excluded). A total of 6 participants will be recruited from each unit for a total of 24 participants. Attrition is expected to be minimal given the inpatient context and previous delivery of CAT with this population. While previous data are not available for formal power analysis, this sample size is anticipated to prove adequate for the detection of medium-large effects though must be considered underpowered and will inform future power analysis.

Specific criteria include:

##### *Inclusion:*

1. A chart diagnosis of a schizophrenia spectrum illness.
2. Capacity to consent or availability of a substitute decision-maker to consent with the assent of the participant.
3. Participant residing on a CAMH inpatient forensic unit (general security)

#### ***Cognitive Adaptation Training (CAT)***

Cognitive Adaptation Training (CAT) is a standardized implementation of environmental supports for improving multiple domains of adaptive functioning including medication adherence, grooming, and activities of daily living in patients with schizophrenia. Environmental supports (signs, checklists, cueing devices) are manual-driven and grounded upon a comprehensive assessment of neurocognitive function and behaviour. Interventions for each functional deficit are based on two dimensions, (1) level of impairment in executive functions (as determined by scores on a set of neurocognitive tests) and; (2) whether the overt behaviour of the individual is characterized more by apathy (poverty of speech, movement, and the inability to initiate and

follow through on behavioural sequences), disinhibition (distractibility and behaviour which is highly cue-driven) or a combination of these styles (based upon scores from the Frontal Lobe Personality Scale (FLOPS)).

According to the CAT model, individuals with poor executive functioning need high levels of structure and more obviously placed environmental cues, while those with somewhat better executive functioning need less structure and more subtle cues. Individuals with apathetic behaviour benefit from environmental supports that cue and sequence behaviour, those with disinhibition benefit most from the removal of distracting stimuli and those with mixed behaviour benefit from a combination of these strategies. Assessment results yield one of six CAT classifications for which interventions can be targeted. These classifications appear in Table 1 below.

**Table 1:** CAT interventions fall into one of the six classifications below.

	Apathy	Disinhibition	Mixed
Poor Executive Functioning	Apathy/Poor	Disinhibited/Poor	Mixed/Poor
Fair Executive Functioning	Apathy/Fair	Disinhibited/Fair	Mixed/Fair

While the full-CAT program targets many areas of adaptive functioning (e.g. shopping, medication management, leisure skills), there is a subset of interventions designed specifically to improve organization and self-care. These goal areas will be the focus of the finCAT approach, modifying the intervention to be more relevant and feasible for an inpatient setting. Problems with dressing/grooming and housekeeping are described and examples of CAT interventions for each of these problems are presented in Table 2 below.

**Table 2:** Problems in adaptive function and examples of CAT interventions

General Problem	Specific Behaviour	CAT Interventions
Laundry	Washes clothing infrequently, runs out of clean clothing.	
 
- Add “do laundry” to weekly activity schedule.
 
- Place signs at the bottom of underwear and sock drawers saying, “If this is the last one, I need to do laundry.”
 

Grooming	Unkempt appearance, shirt not tucked in, hair not combed, etc.	
 
- Place a full-length mirror in an obvious location.
 
- Attach a comb to the mirror with a string and a sign, “Is my hair combed? Is my shirt tucked in?”
 

Cleaning	Throws trash (e.g. wrappers) on floor. Will over fill trash can.	
 
- Place trashcans in plain sight in open areas (particularly in places where wrappers are opened, etc., and trash accumulates on the floor).
 
- Physically prompt use.
 

-----------------	--	--

Once an individual’s CAT classification has been determined, strategies for specific functional problems (dental hygiene, laundry, housekeeping) are chosen from a series of tables. These basic strategies are then altered for strengths or weaknesses (relative to other outpatients with schizophrenia) in the areas of attention, memory, and fine motor skills. For example, for someone with poor attention, the colour of signs can be changed regularly or fluorescent colours can be used to capture attention. For someone with memory problems (particularly those with good auditory attention) audiotapes can be used to sequence behaviour.

CAT interventions are established and maintained in the client’s living space during weekly visits from a CAT therapist/trainer. CAT is a “user-friendly” intervention for both patients and therapists. Acceptance of the interventions has been very high by patients in previous studies. Supplies will be provided within unit contraband protocols.

For CAT on inpatient forensic units, CAT clinicians will (as relevant and possible) meet with unit staff/key supports of clients in the presence of clients and with their permission. They will educate the respective teams about CAT, provide team members with clear indicators of the client’s CAT goals and CAT strategies in place, and encourage them to assist with the reinforcement of the use of CAT tools and strategies.

### *Basic CAT Training*

To further address the barriers to implementing evidence-based practices described above, small educational group meetings will be organized for all individual inpatient teams to educate them on the basic principles of CAT. These meetings will be led by Student OTs familiar with the basics of CAT and repeated on each unit to maximize the number of staff trained. The basic CAT training is a 30-90-minute meeting in which information is provided about the rationale behind CAT and the steps involved. The educational meeting is provided on-site and includes an interactive component by training the team members in administering the Frontal Systems Behaviour Scale (FrSBe) and an opportunity to identify and uphold the goals of CAT supports in a client space.

### **Measures**

#### *Clutter Image Rating Scale (CIRS)*

Room organization will be measured by ratings on the Clutter Image Rating Scale (CIRS; Frost et al., 2008). The CIRS is a 9-picture visual analogue scale used to quantify and standardize the amount of clutter in 3 different living spaces (kitchen, living room, and bedroom). For this project, only the bedroom rating scale will be utilized. The CIRS is used to measure the severity of clutter in compulsive hoarding. It has been shown to be less affected by an over-reporting bias and to have strong inter-observer reliability with a strong participant/experimenter correlation. Before and after photos will be taken of each participant's room. These photos will be rated by 2 blinded student investigators with the mean rating taken.

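### Does the plan need to spell out what the CIRS photo raters are blinded to, given that CAT supports may be visible in the room?

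*Combined protocol and SAP*

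**What the plan says.** All references are to the combined protocol and SAP.

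- **Rating.** Under Clutter Image Rating Scale (CIRS), each room is photographed before and after, and "These photos will be rated by 2 blinded student investigators with the mean rating taken". The scale is anchored to pictures, and the section credits it with strong agreement between observers. No other section defines the blinding or gives a procedure for it.
- **Design.** The Proposed Project describes "The objective of this single group study with pre-post and follow up assessments". One stated use of the results is "to inform future trials with respect to anticipated recruitment and drop-out rates and optimal powering".
- **Schedule.** Table 3 lists CIRS at four assessments: Baseline, Pre-CAT, Post-CAT and Follow-Up. Under Study Design Overview, the four treatment weeks are "followed by two months of maintenance by CAT Unit Champions".
- **Intervention.** Under Cognitive Adaptation Training (CAT), "CAT interventions are established and maintained in the client’s living space". The same section says that "individuals with poor executive functioning need high levels of structure and more obviously placed environmental cues", whereas "those with disinhibition benefit most from the removal of distracting stimuli". One Table 2 example reads "Place trashcans in plain sight in open areas".
- **Analysis.** Data Analysis names CIRS, GAS and the life-skills score as primary variables, compares time points by ANOVA with post hoc tests at the 0.05 level, and reports Cohen's d.

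**The concern.** With one group there is no treatment arm to conceal. Calling the raters blinded protects CIRS only if they cannot tell a before photo from an after photo, and the text does not say that this is meant.

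The intervention also works by placing objects in the space that is photographed. A sign or checklist in view could date the picture. If both raters then expect improvement, averaging them does not help, because the expectation is shared. High agreement between raters does not help for the same reason. Students also appear elsewhere in the study: student occupational therapists lead the basic CAT training, and student investigators run interviews and focus groups. Nothing says that the raters are different people.

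At stake is the before-after effect size for a primary variable. It is meant to feed the powering of later trials, and there is no control group against which a rater effect would show.

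**Working it through.** **1. What the word must mean.** Three features of the plan set side by side: one group, photos from before and after, raters called blinded. There is no arm to hide. Time point is the only thing whose concealment would serve the comparison, so it is the natural reading. What remains unstated is procedure: removing dates, coding and shuffling. There are 24 × 2 = 48 photos if only before and after are taken, or 24 × 4 = 96 if all four CIRS assessments in Table 3 are photographed. Either number can be coded and shuffled at any time before rating.

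**2. How many rooms could be revealing.** The documents do not allow a count.
- Pointing to visibility: more obvious cues for clients with poor executive functioning, and signs and checklists in the room.
- Pointing away: Table 2 gives examples only. A trashcan is an ordinary object. The laundry signs lie at the bottom of drawers. Clients with disinhibition may have items removed. The Safety Protocol bars glass and long strings, which limits the mirror-and-comb example. The framing of the photos is not described.

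**3. Size of a possible shift.** The plan states no figure to reproduce. Let *k* of the 24 rooms be revealing, and let both raters score those rooms *s* points better at Post-CAT and Follow-Up, with no true change.

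- Spurious mean change from Pre-CAT to Post-CAT = (*k*/24) × *s*
- Spurious paired *d* = (*k*/24) × *s* / SD of change

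*k*, *s* and the SD are all assumptions. The SD of change is taken as 1.0 to 2.0 points. The rejection rates come from 40,000 simulated studies per setting with n = 24 and a two-sided paired test at 0.05.

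| *k* | *s* | Spurious mean change | Spurious *d* (SD 2.0 to 1.0) | Chance of p < .05 (SD 2.0 to 1.0) |
|---|---|---|---|---|
| 6 | 0.25 | 0.0625 | 0.03 to 0.06 | 5.2% to 5.9% |
| 6 | 0.5 | 0.125 | 0.06 to 0.13 | 5.9% to 8.2% |
| 12 | 0.25 | 0.125 | 0.06 to 0.13 | 5.9% to 8.9% |
| 12 | 0.5 | 0.25 | 0.13 to 0.25 | 8.7% to 19.7% |
| 24 | 0.25 | 0.25 | 0.13 to 0.25 | 9.0% to 21.7% |
| 24 | 0.5 | 0.5 | 0.25 to 0.50 | 21.8% to 65.0% |

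A three-time-point repeated-measures ANOVA gives similar rates, from 5.1% to 68.8%. For Post-CAT against Follow-Up the shift cancels if the same supports stay in view, and the rate stays at about 5%.

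The range runs from nothing to severe, and the assumed inputs alone decide where in it the study falls. The sign is assumed too. If a rater counted added signs or objects as clutter, *s* would be negative and the improvement would be understated.

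**4. Whether added text would remove the shift.** Coding, shuffling and fixed framing remove cues from dates and order. They leave the supports in the picture, so (*k*/24) × *s* is unchanged. Covering the supports only where they occur would itself mark the after photos.

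A repeat analysis without the revealing rooms has two weaknesses.
- It selects on a feature that arises after baseline and reflects how much treatment was put in place and kept up.
- It is imprecise. The 95% half-width for mean change is t(0.975, *m* − 1)/√*m* in SD units: 0.42 for *m* = 24, 0.50 for 18, 0.64 for 12, and 2.571/√6 = 1.05 for 6. With all 24 rooms revealing, none remain.

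Take *k* = 12, *s* = 0.5 and SD 1.0. The all-rooms estimate should exceed the 12-room estimate by 0.25 SD. The standard error of that difference is √(1/12 − 1/24) = 0.20 SD, so twice the standard error is 0.41 SD. The check would usually miss the bias it looks for.

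Asking raters to guess the time point is no better as a test, because a correct guess may simply reflect a tidier room.

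**The case for a change.** The strongest case for a change is that the gap is in the text, that closing it costs a few lines, and that the unstated part is what gives the word blinded its meaning here. If time point is intended, saying so is nearly free, and coding and shuffling are needed to achieve it. CIRS is also the only primary variable whose raters are described as blinded, so readers may rely on it more than on the others, and its effect size is meant to be carried forward.

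Much of this stands. The text is silent, supports could reveal the time point in some rooms, and neither averaging nor good agreement would remove a shared expectation. It is sound practice to code and shuffle the photos before rating and to report the raters' other roles.

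It does not amount to a defect in the plan. Blinded rating is already planned, and the handling steps carry it out without altering it. The threat that goes beyond wording, visible supports, would remain afterwards. CIRS is also the best protected of the three primary variables: GAS is scored by agreement between the clinician and the case manager, and the life-skills ratings come from unit nurses outside the delivery of finCAT. Lastly, a pre-post effect without a control already mixes treatment with time and other influences on the unit, and tighter masking of photos would not separate them.

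**Conclusion.** No change to the plan is needed. The missing detail is a gap that the study team can fill sensibly when it prepares the photos, because time point is the only meaningful target of blinding in this design. What is left is a limitation to acknowledge when CIRS is reported: some Post-CAT and Follow-Up photos may show supports, so masking may be partial, and the before-after change could be biased in either direction.

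Its size is unknown. On the assumed inputs it is negligible when few rooms are revealing (*d* of 0.03 to 0.06 for 6 rooms and a 0.25-point shift). It becomes large only if most or all rooms are revealing and both raters lean the same way by half a point. Post-CAT against Follow-Up is essentially unaffected if the supports stay in place.

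The consequences are limited as well. The Participants section calls the sample underpowered, the study is one of feasibility, and no confirmatory decision rests on the CIRS test. This conclusion assumes that the raters are in fact kept from knowing the time point by ordinary photo handling.
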